#### 4.2.2 Secondary Study Endpoints

Secondary endpoint: steps per day, hemoglobin A1c levels, diagnosis of diabetes, engagement score based on dDPP data logs and lesson completions, and patient demographics, social determinants, and other baseline descriptive data

#### 4.2.3 Exploratory Endpoints

## 5 Study Enrollment and Withdrawal

### 5.1 Inclusion Criteria

In order to be eligible to participate in this study, an individual must meet all of the following criteria:

Provider Inclusion Criteria: (a) Fulltime primary care provider (MD/DO, NP) practicing at the participating FHCs or FGPs and, (b) Provide care to at least five patients with a diagnosis of pre-diabetes.

Patient Inclusion Criteria:

In order to be eligible to participate in this study, an individual must meet all of the following criteria:

1. 18 years or older,  $BMI \geq 25 \text{ kg/m}^2$  ( $> 22 \text{ kg/m}^2$  if self-identified as Asian)
2. A diagnosis of prediabetes (either diagnosis of prediabetes or an HbA1C level of 5.7%-6.4% in past 18 months)
3. Baseline self-test a1c value of 5.4 to 6.4
4. Safe to engage in moderate physical exercise (as determined by their PCP)

CONFIDENTIAL

This material is the property of the NYU School of Medicine and NYU Langone Health. Do not disclose or use except as authorized in writing by the study sponsor Behavioral Intervention Template Version: 11 January 2019

5. Sufficient English to be able to complete the enrollment process
6. Has app capable device with data to use the dDPP application and receive text messages
7. NYU Langone Health Patient with assigned PCP on EPIC/EHR

## **5.2 Exclusion Criteria**

An individual who meets any of the following criteria will be excluded from participation in this study:

Provider Exclusion Criteria: Refuse to participate

Patient Exclusion criteria:

An individual who meets any of the following criteria will be excluded from participation in this study:

1. Diagnosed with diabetes
2. Patients whose weight may vary considerably over the study's timeframe for reasons other than the intervention (e.g. cancer, pregnancy, ascites, severe CHF)
3. Patients with severe psychiatric disease or dementia
4. Active health condition that prevents them from engaging in moderate exercise

## **5.3 Vulnerable Subjects**

Providers (MD/DO, NP) practicing at the participating FGP, who are employees of the hospital system will be interviewed as part of Phase 2 of the study. They will not be affected by their decision to participate in this study. Their participation will not affect their employment, reputation, or be linked to their employment record.

Study personnel involved in recruitment do not have any supervisory role or performance evaluation. Consenting process emphasizes voluntary participation, minimizes any coercion and location is appropriate to ensure privacy and maintenance of confidentiality of the discussion. Consenting will be done in person, via email, or part of anonymous survey. Risks of breach of confidentiality are minimized. Investigator will ensure subjects full understanding of research and minimize undue influence. The research will not affect employment or performance evaluation.

## **5.4 Strategies for Recruitment and Retention**

**Provider participants** will be identified based on their role at the study clinics and eligibility criteria. The study will be presented to the providers by the study team. A study team member will verbally consent the provider and scheduled a time for workflow assessment, group adaptation session, and live-usability tests. The participants will be given a key information sheet that outlines their research participation. The providers may be verbally consented and interviewed over video call due to covid19 restrictions.

### **Patient participants (Phase 2 and 3)**

CONFIDENTIAL

This material is the property of the NYU School of Medicine and NYU Langone Health. Do not disclose or use except as authorized in writing by the study sponsor Behavioral Intervention Template Version: 11 January 2019

EPIC workbench report will be run once a day to screen patient subjects for eligibility for Phases 2 and 3 of the study. Once a list of potential subjects are generated, they will be sent a mychart recruitment letter, and contacted via phone call. (Scripts included) The list of prediabetic patients are obtained from EPIC.

If a patient is recruited through provider referral, or clinicaltrial.gov, they will be emailed the same recruitment letter via sendsafe email.

Providers will be able to refer patients via secure chat in EPIC to the research assistant or email the dedicated study email address, [[contact]](mailto:[contact]), with the patient's best contact information via SendSafe email.

Potential subjects will be recruited electronically via redcap consent form and esignature. Each subject will be scheduled for a video visit with a study team member.

Signed informed consent will be obtained from participants who meet the study eligibility criteria. Subject will be provided ample time to review the consent form. A research team member will review each section with the subject, ask the subject if they understand each section, and clarify any questions they may have. The subject and the person obtaining consent will sign and date the consent form. The subject will get a copy of the signed informed consent document via email. Informed consent will be considered an ongoing process throughout the study, and subjects' questions regarding their rights and responsibilities will be addressed whenever they occur.

Due to COVID-19 and to keep the safety of both our research team and research subjects, we will be collecting consent via RedCap. A trained Research staff member will schedule a time with eligible interested participants to go over the informed consent via telephone. After going over the informed consent via telephone, research staff member will also send the consent via a RedCap link where the participant has the opportunity to read the consent and sign electronically, confirming that they read and understood the consent. Research staff member will also document on RedCap the time and date of the telephone consent and note that the consent process was done via telephone due to COVID-19.

Research assistants will recruit participant in person at participating FGP primary care clinics. Eligible patients will be identified prior to the appointments or clinical staff will refer patients to the research assistant during the recruitment shift. If patient is eligible, they will be consented in a private area of the clinic. Patients will be able to sign the research consent form on a NYU Langone encrypted iPAD or laptop. The consenting and onboarding procedure will be the same as for those who are onboarded virtually. In-person recruited patients will be tested for their HbA1c values immediately after the consent to verify eligibility.

Any information sent by email will utilize Send Safe email.

A waiver of consent is requested since the study involves using identifiable private information and presents no more than minimal risk to the subjects since the data will be stored in a HIPAA compliant database and only authorized study staff will have access to the data. The conduct of the study could not practicably be carried without the waiver because we are collecting the following PHI including name, date of birth, address, telephone number, diagnosis history, and medical record number. Data will be retained electronically for 3 years after close-out and 5 years after final reporting/publication. The rights and welfare of the participants will be protected

CONFIDENTIAL

This material is the property of the NYU School of Medicine and NYU Langone Health. Do not disclose or use except as authorized in writing by the study sponsor Behavioral Intervention Template Version: 11 January 2019

by emphasizing to them that the quality of their medical care will not be adversely affected if they decline to participate in this study.

#### **5.4.1 Use of DataCore/Epic Information for Recruitment Purposes**

Recruitment will be done via both direct and indirect contact. This study will utilize EPIC to identify subjects. Research staff will run reports once a day through EPIC reporting workbench through the course of the study to obtain a list of potential subjects meeting eligibility criteria at NYU Langone sites. All members of the study team (PI, study coordinator, study team members) will have access to the EPIC search results.

We will collect the following additional PHI: Name, date of birth, address, telephone number, diagnosis history, medical record number. Data will be retained electronically for 3 years after close-out, 5 years after final reporting/publication. No records will be destroyed without the written consent of the sponsor, if applicable. It is the responsibility of the sponsor to inform the investigator when these documents no longer need to be retained. NYU Langone MCIT will remove data from applicable sources at the time periods listed above.

Any recruitment information sent by email will utilize Send Safe email. (Refer to appendices)

Once potential subjects have been identified, the treating physician (TP) agrees to permit study team to directly contact potential subjects on behalf of TP.

Once contact is made, IRB approved recruitment language will be used to communicate the reason they are being contacted and subjects will be asked if they are interested in participating in this specific study. If the potential subjects agree, the study team will provide the subjects with information regarding the next steps for participation.

If a subject requests information regarding opting out of further recruitment for all research, subjects will be directed to contact [[contact]](mailto:[contact]) or [name].

#### **5.5 Duration of Study Participation**

Phase 2 and Phase 3 patient participants will be asked to participate in the study for 18 Months.

#### **5.6 Total Number of Participants and Sites**

For phase 2:

Recruitment will end when approximately 40 patient participants are enrolled. It is expected that approximately 40 participants will be enrolled in order to produce 40 evaluable participants.

Recruitment will end when approximately 40 provider participants are interviewed around usability testing and workflow adaptation.

For phase 3:

CONFIDENTIAL

This material is the property of the NYU School of Medicine and NYU Langone Health. Do not disclose or use except as authorized in writing by the study sponsor Behavioral Intervention Template Version: 11 January 2019

Recruitment will end when approximately 432 participants are enrolled. It is expected that approximately 432 participants will be enrolled in order to produce 432 evaluable participants.

Recruitment will end when approximately 20-40 provider participants are surveyed around the provider-dashboard and other study components.

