the study team at each time point to complete testing. HbA1C testing kits have been shown in prior studies to be safe and equivalent to laboratory testing, and are increasingly used in pragmatic digital studies to avoid unnecessary burden on participants.

For continuous outcomes including weight reduction, mean steps per day, and reduction in HbA1C level, we will use generalized estimating equations (GEE) to compare treatment arms with time and intervention as a fixed effect and practice as a random effect, to adjust for clustering of patients within practices. Participant demographic characteristics including age, gender, race/ethnicity and other potential confounders determined as a priori will be controlled for in GEE. We will also collect patient characteristics, such as demographic information, social determinants, and other baseline descriptive data, from the EHR. For the second outcome of 7% weight-loss achievement, we will use a similar GEE model with a logit link function. We will report the estimated effect of intervention and its associated 95% confidence interval calculated by using the robust variance estimator. We will also report the intra-cluster correlation and time effect from the fitted model.

Missing data frequently occur in pragmatic clinical trials with long follow-up. To supplement missing HbA1C and weight data from patients, we will conduct EHR data extractions. Our data analyst will run a query based on the appropriate time windows per patient to pull values and dates for HbA1C and weight, respectively. Standard GEE will be unbiased only if data are missing completely at random (MCAR), which rarely occurs in practice. Thus, we will apply weighted GEE to accommodate the more realistic missing at random (MAR) assumption. Due to the large number of clinics, providers, and patients, we expect balance by study arm over patient, provider, and clinic characteristics. In case of imbalance, however, we will investigate propensity score weighting to adjust the observed differences.

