### **10.5 Sample Size**

The primary hypothesis is whether weight change among patients affiliated with practices enabled with the dDPP-EHR tool suite is significantly different from weight change in patients using the dDPP in conjunction with usual care. Based on the ~40% increase in dDPP lesson completion (17 vs 12) among patients reporting high levels of provider engagement (post hoc analysis conducted by [name] on her GOALS dDPP), we estimated a range of expected effect sizes from 20-60% in lesson completion in the dDPP-EHR intervention arm (approximately equivalent to completing 2-8 more Noom dDPP lessons). We estimate that this increased lesson completion will translate into at least an additional 2.0 kg of weight loss in the intervention (dDPP-EHR) arm, a conservative estimate considering Noom's dDPP trial observed a 4 kg of weight loss difference (6.6 vs 2.4 kg) with the completion of 6 additional dDPP lessons and GOALS noted a 2.5 kg weight loss difference with 5 additional lessons completed. We estimate the 1 year weight loss will be 4.5 kg and 2.5kg for the dDPP-EHR and dDPP alone approaches, respectively. This is also conservative compared to the 6.2 vs 3.7 kg weight loss difference observed in the post-hoc analysis of GOALS dDPP participants reporting high vs. low provider engagement without any data integration (and the presumed enhanced lesson completion it would facilitate). We also assume a standard deviation of weight loss (at 1 year) of 5 kg based on data from Noom and another GOALS dDPPs. Empirical EHR data indicate that the average annual number of distinct eligible patients is approximately 200 per clinic. The proposed study sample provides 97% power to detect a conservative estimate of 30% increase in Noom dDPP session completion and a 2kg increased 12-month weight loss in the intervention arm if we have 200 patients/arm (a

CONFIDENTIAL

This material is the property of the NYU School of Medicine and NYU Langone Health. Do not disclose or use except as authorized in writing by the study sponsor Behavioral Intervention Template Version: 11 January 2019

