conservative recruitment goal considering our prior experience). The same sample provides 93% power to detect a difference of 1.75 kg between arms. As an additional sensitivity analysis, we also calculated estimated power if only 80% of the anticipated patients/clinic and clinics/arm were collected (i.e., 160 patients/arm). This sample still provides 94% power to detect the expected difference of 2 kg between arms. Therefore, we expect to have adequate statistical power to detect a range of differences between arms (assuming two-sided tests with significance level of alpha = 0.05).

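### Section 5.6 counts all 432 enrolled patients as evaluable, which conflicts with the plan's own expectation of missing data, and section 10.5 makes no allowance for attrition

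*Combined protocol and SAP*

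**What the plan says.** Section 5.6 sets the phase 3 size: "It is expected that approximately 432 participants will be enrolled in order to produce 432 evaluable participants". It uses the same form of words for the 40 patients of phase 2.

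Other sections bear on whether that can happen:

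- Section 5.5 asks patients to take part for 18 months. The weight difference used for power is at 12 months.
- Sections 5.7.1 and 5.7.2 allow withdrawal at any time, end data collection at that point, and keep the data gathered before it.
- Section 10.4.2 says: "Missing data frequently occur in pragmatic clinical trials with long follow-up". Section 10.4.1 says the same. Both add that data are rarely missing completely at random and plan weighted GEE. Section 10.4.2 also plans outreach to patients with missing data and extraction of weights from the EHR.

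Section 10.5 gives the power. The effect is 2 kg: "We estimate the 1 year weight loss will be 4.5 kg and 2.5kg for the dDPP-EHR and dDPP alone approaches, respectively". On spread: "We also assume a standard deviation of weight loss (at 1 year) of 5 kg". The main case is 97% for "2kg increased 12-month weight loss in the intervention arm if we have 200 patients/arm", with 93% for 1.75 kg. For a smaller sample, "we also calculated estimated power if only 80% of the anticipated patients/clinic and clinics/arm were collected", which it puts at 160 patients per arm with 94% power for 2 kg.

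The current design has three arms, 432 patients and 1:2 allocation (sections 4.1 and 10.4.1), with 144 in the control arm (Protocol Summary).

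**The concern.** The number enrolled and the number evaluable are different quantities, and section 5.6 is where a loss allowance would normally appear. Setting them equal says that no patient will be lost over at least 12 months. The analysis sections expect the opposite. No expected loss rate appears in the document, so a reader cannot tell what evaluable number the trial was planned around, or judge later whether retention met plan.

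The precision of the 12-month comparison depends on the weights actually obtained. If section 10.5 allowed for loss, the sentence in 5.6 would be only careless wording. It does not. Its reduced-sample case concerns patients per clinic and clinics per arm, and it assumes two equal arms, which this trial does not have.

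**Working it through.** **Inputs.** Difference 2 kg or 1.75 kg, SD 5 kg, two-sided alpha 0.05, and 200 or 160 per arm, all from section 10.5. Total 432 and 1:2 allocation are from section 10.4.1, and 144 controls from the Protocol Summary. Three equal arms of 144 follow if the two intervention arms are the same size (432 − 144 = 288; 288 / 2 = 144). The documents give no loss rate, so 10-30% is an assumed range.

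**Formula.** For arms of n1 and n2, SE = 5 × √(1/n1 + 1/n2). Power is the probability that a noncentral t variable, with n1 + n2 − 2 degrees of freedom and noncentrality difference/SE, falls outside the two-sided 5% critical values. Patients are treated as independent.

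**The plan's own figures.**

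- 200 per arm, 2 kg: SE = 5 × √(2/200) = 0.50, noncentrality 4.0, power 97.9% (stated 97%).
- 200 per arm, 1.75 kg: noncentrality 3.5, power 93.7% (stated 93%).
- 160 per arm, 2 kg: SE = 0.559, noncentrality 3.58, power 94.6% (stated 94%).

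All three reproduce with no attrition term. None of them uses 432.

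**The three-arm design.** Each patient without a 12-month weight is treated as wholly lost, and loss is equal across arms.

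| Assumed loss | Pooled intervention v control (n) | 2 kg / 1.75 kg | One intervention arm v control (n) | 2 kg / 1.75 kg |
|---|---|---|---|---|
| 0% | 288 v 144 | 97.4% / 92.8% | 144 v 144 | 92.3% / 84.1% |
| 10% | 259 v 130 | 96.0% / 90.1% | 130 v 130 | 89.5% / 80.3% |
| 20% | 230 v 115 | 93.7% / 86.4% | 115 v 115 | 85.6% / 75.3% |
| 30% | 202 v 101 | 90.5% / 81.7% | 101 v 101 | 80.8% / 69.7% |

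Worked cell, pooled at 20%: SE = 5 × √(1/115 + 1/230) = 0.571; 2 / 0.571 = 3.50; power 93.7%.

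**Interval width.** The 95% half-width for the pooled contrast is 1.96 × 0.510 = 1.00 kg at no loss and 1.96 × 0.571 = 1.12 kg at 20% loss.

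**Separating the two causes.** For one arm against control and 2 kg, power goes from 97.9% (200 per arm) to 92.3% (144 per arm, no loss) and then to 85.6% (115 per arm, 20% loss). The first step, 5.6 points, is arm size. Only the second, 6.7 points, is attrition.

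**The case against.** A reader might infer that the quoted powers rest on 432 evaluable patients and fail once patients are lost. The documents do not support that. The powers are computed at 200 and 160 per arm, so correcting 5.6 changes none of their inputs.

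Power also depends on how many patients are analysed, not on why the number fell. The 160-per-arm case totals 320, which is 20% below 400 and about 26% below 432 (1 − 320/432), and it gives 94%. For the pooled contrast, the stated 97% and 93% agree with the three-arm design at no loss, and 94% agrees with it at 20% loss. This stands as arithmetic for 2 kg. It does not supply an attrition assumption: the case is worded as a shortfall in patients and clinics, it assumes two equal arms, and it gives no figure for 1.75 kg.

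It can also be said that evaluable is undefined and that the primary set is all randomized patients (section 10.3). Weights are scheduled at baseline and 3, 6, 9 and 12 months, EHR values fill gaps, and weighted GEE uses partial records, so a patient without a 12-month reading still contributes. This stands too, and it is why the table is a worst case. It does not rescue the sentence, which presents enrolment as the means of producing evaluable patients and so treats the two as distinct.

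Finally, 432 could be read as 400 plus a margin of 32. The plan never says so, and 5.6 rules it out by calling all 432 evaluable.

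**Conclusion.** The point holds in a limited form. Section 5.6 states zero loss, the rest of the plan expects loss, and section 10.5 has no attrition allowance. No stated power is miscalculated.

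The size is modest. Under the worst-case treatment, 10-30% loss leaves power for 2 kg at 96% to 91% for the pooled contrast and 90% to 81% for one intervention arm against control. Loss in this range does not by itself take power for 2 kg below 80%, so a conclusion that the trial is underpowered for its planned effect would go too far. The smaller effect of 1.75 kg is more exposed: at 20% loss it has 86% pooled and 75% for a single arm.

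The single-arm gap at no loss (92% / 84% against the stated 97% / 93%) comes from arms of 144 instead of 200 and should not be put down to attrition. Which column applies depends on the primary contrast, which the plan leaves open: sections 10.1 and 10.5 describe two groups, while the Protocol Summary compares three arms.

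The figures assume SD 5 kg, two-sided 0.05, equal loss across arms, independent patients and equal intervention arms. The loss rates are illustrative.

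**What to change.** 1. In section 5.6, give two numbers: 432 enrolled, and the number expected to be evaluable at the sponsor's own anticipated loss rate, with evaluable defined (for example, having a 12-month weight from the scale or the EHR). At 10%, 20% and 30% loss, 432 enrolled leaves about 389, 346 and 302.
2. In section 10.5, restate power at that number for the three-arm 1:2 design. Name the primary contrast (pooled or single arm against control) and show a 10-30% loss range. Keep the 160-per-arm case only if it is labelled as a recruitment shortfall.

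Enrolment, design and analysis stay as they are. The cost is a few sentences and a slightly less favourable stated size and power.

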## **5.7 Participant Withdrawal or Termination**

### **5.7.1 Reasons for Withdrawal or Termination**

Participants are free to withdraw from participation in the study at any time upon request. An investigator may terminate participation in the study if:

- Any clinical adverse event (AE), laboratory abnormality, or other medical condition or situation occurs such that continued participation in the study would not be in the best interest of the participant
- The participant meets an exclusion criterion (either newly developed or not previously recognized) that precludes further study participation

